- 10) Give the parent / guardian a diary card (DC3).
- 11) Remind the parent / guardian to expect a telephone call 8 days after Visit 3 and to bring back the diary card when they return for Visit 4 at a specified date and time.
- 12) Remind the parent / guardian to notify the site in case of an SAE.
- 13) Complete the relevant CRFs for this visit.

Telephone Call 3 (8 days [+2 days] after Visit 3)

Refer to steps in Telephone Call 1.

Visit 4 (30 [+21] days after Visit 3): Collection of Safety Information and Blood Sample

- 1) Collect and review the diary card (DC3) with the parent / guardian, including any AEs, medications, or therapy that occurred since vaccination. If an SAE, including an AESI, has occurred, follow the instructions in [Section 10](#) for reporting it.
- 2) Review temporary contraindications for blood sampling. Ensure the subject has not had any antibiotics within the previous 72 hours (3 days).
- 3) Collect 3 mL of blood (BL0003) (see [Section 7](#) for detailed instructions regarding the handling of blood samples).
- 4) Give the parent / guardian a memory aid to record SAE and MAAEs from Visit 4 until the 6-month follow-up phone call.
- 5) Remind the parent / guardian to notify the site in case of an SAE.

- 6) Complete the relevant CRFs for this visit and trial termination record^a.

Safety Follow-up Telephone Call 4 (180 [+30] days after Visit 4): Collection of SAEs

- 1) Ask the parent / guardian if the subject has experienced any SAE and / or MAAE since the last study visit. If an SAE, including an AESI, has occurred, follow the instructions in [Section 10](#) for reporting it.
- 2) Complete the relevant CRFs for this visit.

This call must be made by a qualified person.

A follow-up visit outside the scope of this study protocol can be arranged depending on the information recorded during the phone call.

5.1.4.2 Visit Procedures for Group 3 and Group 4

Visit 1 (17 to 19 months of age): Inclusion, Randomization, Blood Sampling, and Vaccination

- 1) Give the subject's parent / guardian information about the study, obtain written informed consent, and provide a signed copy.
- 2) Check inclusion and exclusion criteria for eligibility.
- 3) Collect demographic data.
- 4) Obtain and collect verbal medical history about the subject, including ongoing medication.

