 - Meningococcal vaccine (MenACYW conjugate vaccine or Menactra[®]): inject IM into the anterolateral area of the thigh, preferably the right thigh.
- 8) Observe the subject for 30 minutes and record any AEs in the source document.
- 9) Give the parent / guardian a diary card (DC2).
- 10) Remind the parent / guardian to expect a telephone call 8 days after Visit 2 and to bring back the diary card when they return for Visit 3 at a specified date and time.
- 11) Remind the parent / guardian to notify the site in case of an SAE.
- 12) Complete the relevant CRFs for this visit.

Telephone Call 2 (8 days [+2 days] after Visit 3)

Refer to steps in Telephone Call 1.

Visit 3 (30 [+21] days after Visit 2): Collection of Safety Information and Blood Sample

- 1) Collect and review the diary card (DC2) with the parent / guardian, including any AEs, medications, or therapy that occurred since vaccination. If an SAE, including an AESI, has occurred, follow the instructions in [Section 10](#) for reporting it.
- 2) Review temporary contraindications for blood sampling. Ensure the subject has not had any antibiotics within the previous 72 hours (3 days).
- 3) Collect 3 mL of blood (BL0002) (see [Section 7](#) for detailed instructions regarding the handling of blood samples).
- 4) Give the parent / guardian a memory aid to record SAE and MAAEs from Visit 3 until the 6-month follow-up phone call.
- 5) Remind the parent / guardian to notify the site in case of an SAE.
- 6) Complete the relevant CRFs for this visit and trial termination record.

Safety Follow-up Telephone Call 4 (180 [+30] days after Visit 4: Collection of SAEs

- 1) Ask the parent / guardian if the subject has experienced any SAE and / or MAAE since the last study visit. If an SAE, including an AESI, has occurred, follow the instructions in [Section 10](#) for reporting it.
- 2) Complete the relevant CRFs for this visit.

This call must be made by a qualified person.

A follow-up visit outside the scope of this study protocol can be arranged depending on the information recorded during the phone call.

Follow-up of subjects with Related AEs or with AEs That Led to Study/Vaccination Discontinuation:

A subject who experiences an AE (whether serious or non-serious) during the study must be followed until the condition resolves, becomes stable, or becomes chronic (even after the end of the subject's participation in the study) if *either* of the following is true:

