12.2.3.1 Per-Protocol Analysis Set 1 (PPAS1)

Serology obtained 30 days after the vaccination visit at 6 months of age for all antigens will be used for immunogenicity analyses of infant stage of study.

PPAS1 will be a subset of FAS1. The subjects presenting with at least one of the following relevant protocol deviations will be excluded from the PPAS1:

- Subject did not meet all protocol-specified inclusion criteria or met at least one of the protocol-specified exclusion criteria
- Subject did not complete the vaccination schedule
- Subject received a vaccine other than the one that he / she was randomized to receive
- Preparation and / or administration of vaccine was not done as per-protocol
- Subject did not receive vaccine in the proper time window
 - Group 1 and Group 2
 - Visit 1: 24 to 32 weeks of age
- Subject did not provide a post-dose serology sample in the proper time window or a post-dose serology sample was not drawn
 - Group 1 and Group 2
 - Blood Sampling 0002A: Visit 1 + 30 days (± 21 days)
- Subject received a protocol-prohibited therapy / medication / vaccine (reportable concomitant medication of category 2 and / or category 3)
- Subject had other protocol violations that affected the subject's immune response, as determined by the clinical team before locking the database.

In addition to the reasons listed above, subjects will also be excluded from the PPAS1 if their serology sample did not produce a valid test result (i.e., results for all antigens are missing).

Vaccine correctness required by the PPAS1 includes not only the dose of MenACYW conjugate vaccine or MENVEO® but also the concomitant vaccines (DTaP, IPV, Hib, PCV13, Rotavirus, hepatitis B) as scheduled.

In the event of a local or national immunization program with a pandemic influenza or coronavirus vaccine, subjects who receive 1 or more doses of a pandemic influenza or coronavirus vaccine at any time during the study will not be withdrawn from the study.

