Study timelines (days)	D0	Visit 1 +8 days	Visit 1 +30 days	Visit 3 -14 days	≥6 months post-Visit 1	Visit 3 +8 days	Visit 3 +30 days	Visit 3 +180 days
Time windows (days)		+2 days	+21 days			+2 days	+21 days	+30 days
Informed consent	X							
Inclusion/exclusion criteria	X							
Collection of demographic data	X							
Medical history	X							
Physical examination (including temperature measurement) **	X				X			
Contact interactive response technology (IRT) system for randomization/allocation of subject number/vaccine group assignment	X							
Review of temporary contraindications for blood sampling††	X		X		X		X	
Blood sampling (BL) (3 mL)	BL0001‡‡		BL0002A§§		BL0002B‡‡****		BL0003	
Review of warning and precautions to vaccinations	X				X			
Review of contraindications to subsequent vaccinations and conditions for withdrawal†††					X			
Contact IRT system for vaccine assignment	X				X			
Vaccination with MenACYW conjugate vaccine or MENVEO®	X				X			
Vaccination with routine pediatric vaccines‡‡‡	X§§§				X		X****	

Visit (V) / Contact	Visit 1	Telephone Call (TC) 1*	Visit 2	TC 2†	Visit 3	TC 3*	Visit 4	TC 4 Follow-up contact‡
Approximate age of subjects	6 to 7 months§		7 to 8 months	11.5 to 12.5 months	12 to 13 months		13 to 14 months	18 to 19 months
Study timelines (days)	D0	Visit 1 +8 days	Visit 1 +30 days	Visit 3 -14 days	≥6 months post-Visit 1	Visit 3 +8 days	Visit 3 +30 days	Visit 3 +180 days
Time windows (days)		+2 days	+21 days			+2 days	+21 days	+30 days
Immediate surveillance (30 minutes)	X				X			
Diary card provided	DC1		DC2		DC3			
Telephone Call		X		X		X		X
Diary card reviewed and collected			DC1		DC2		DC3	
Recording of solicited injection site and systemic reactions†††	X				X			
Recording of unsolicited adverse events	Recorded from D0 to D30 after each vaccination visit							
Reporting of SAEs (including AESIs) and MAAEs****	To be reported throughout the study period							
Collection of reportable concomitant medications	X		X		X		X	
Memory Aid (MA) provided							X\$\$\$\$	
Completion at End of study							X	

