†††Physical examination should be performed on the basis of relevant medical history at the time of the visit according to the investigator's clinical judgment. Temperature should be measured before each vaccination and recorded in the source documents.

†††In children immunized with PedvaxHIB® at 2 and 4 months of age, a third dose of Hib vaccine at 6 months of age is not required.

§§§Routine pediatric vaccines recommended at this age are to be given as per standard of care, and will not be provided by the Sponsor.

****PCV13 will not be provided by the Sponsor. PCV13 may be given as per standard of care outside of the study during the last study visit after completing all the study procedures (Visit 4).

††††Solicited injection site and systemic reactions will be recorded from D0 through D07 after each vaccination visit.

††††AESIs will be collected throughout the trial as SAEs to ensure that the events are communicated to the Sponsor in an expedited manner, and followed up until the end of the follow-up period or resolution, as per the assigned causality.

§§§§The memory aid will be used only for the recording of SAEs (including AESIs) and MAAEs from Visit 4 to the 6-month follow-up phone call (TC4).

Table 3.4: Table of Study Procedures – Group 3 and Group 4

Phase III Study, 3 Visits, 2 Vaccination visits, 2 Blood Samples, 10-month Duration per Subject

Visit / Contact	Visit 1	TC 1*	Visit 2	TC 2*	Visit 3	TC 3 Follow-up contact†
Approximate age of subjects	17 to 19 months		20 to 23 months		21 to 24 months	27 to 30 months
Study timelines (days)	D0	Visit 1 +8 days	≥3 months post-Visit 1	Visit 2 +8 days	Visit 2 +30 days	Visit 2 +180 days
Time windows (days)		+2 days		+2 days	+21 days	+30 days
Informed consent	X					
Inclusion/exclusion criteria	X					
Collection of demographic data	X					
Medical history	X					
Physical examination (including temperature)‡	X					
Randomization/allocation of subject number	X					
Review of temporary contraindications for blood sampling§	X				X	
Blood sampling (BL) (3 mL)	BL0001**				BL0002	
Review of warning and precautions to vaccinations	X		X			
Review of contraindications to subsequent vaccinations and conditions for withdrawal††			X			
Contact IRT system for vaccine assignment	X		X			
Vaccination with MenACYW conjugate vaccine or Menactra®	X		X			
Immediate surveillance (30 minutes)	X		X			
Diary card provided	DC1		DC2			
Telephone Call		X		X		X
Diary card reviewed and collected			DC1		DC2	

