5.2.3.2 Per-Protocol Analysis Set 2 (PPAS2)

During the second year of life, the immunogenicity analyses for various antigens will be performed on serology obtained 30 days after the given antigen administration if blood collection is planned at that time.

PPAS2 will be a subset of FAS2. The subjects presenting with at least one of the following relevant protocol deviations will be excluded from the PPAS2:

- Subject did not meet all protocol-specified inclusion criteria or met at least one of the protocol-specified exclusion criteria
- Subject did not complete the vaccination schedule including the infant and the second year of the study:
 - Group 1 and Group 2: Up to 12-13 month vaccinations, including the infant schedule
 - Group 3 and Group 4: Up to 23 month vaccinations
- Subject received a vaccine other than the one that he / she was randomized to receive
- Preparation and / or administration of vaccine was not done as per-protocol
- Subject did not receive vaccine in the proper time window
 - Group 1 and Group 2
 - Visit 3: 12 to 13 months of age
 - Group 3 and Group 4
 - Visit 2: 20 to 23 months of age
- Subject did not provide a post-dose serology sample in the proper time window or a post-dose serology sample was not drawn
 - Group 1 and Group 2
 - Blood Sampling 0003: Visit 4 (Visit 3 + 30 days [± 21 days])
 - Group 3 and Group 4
 - Blood Sampling 0002: Visit 3 (Visit 2 + 30 days [± 21 days])

- Subject received a protocol-prohibited therapy / medication / vaccine (reportable concomitant medication of category 2 and / or category 3)
- Subject had other protocol violations that affected the subject's immune response, as determined by the clinical team before locking the database

In addition to the reasons listed above, subjects will also be excluded from the PPAS if their serology sample did not produce a valid test result (i.e., results for all antigens are missing).

Vaccine correctness required by the PPAS2 includes not only the 2 doses of MenACYW conjugate vaccine, MENVEO®, or Menactra® but also, for subjects in groups 1 and 2, the concomitant vaccines (MMR, Varicella) as scheduled in the second year of life.

In the event of a local or national immunization program with a pandemic influenza vaccine or coronavirus vaccine, subjects who receive 1 or more doses of a pandemic influenza vaccine or coronavirus vaccine at any time during the study will not be withdrawn from the study.

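### PPAS2, the set behind both non-inferiority tests, accepts post-dose-2 blood from Day 9, while the visit schedule allows it only from Day 30

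*SAP*

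**What the plan says.** **PPAS2 rule.** For Groups 1 and 2, SAP 5.2.3.2 gives "Blood Sampling 0003: Visit 4 (Visit 3 + 30 days [± 21 days" and, for Groups 3 and 4, "Blood Sampling 0002: Visit 3 (Visit 2 + 30 days [± 21 days". Protocol 12.2.3.2 has the same ± 21 days in both places.

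**Schedule.** Protocol 5.1.4.1 heads the Group 1 and 2 visit "Visit 4 (30 [+21] days after Visit 3): Collection of Safety Information and Blood Sample", and 5.1.4.2 heads the Group 3 and 4 visit "Visit 3 (30 [+21] days after Visit 2): Collection of Safety Information and Blood Sample". The procedure tables agree in both documents. SAP Table 3.3 puts Visit 4 at "Visit 3 +30 days" and SAP Table 3.4 puts Visit 3 at "Visit 2 +30 days", each with +21 days in the window row. The protocol's Tables of Study Procedures read the same.

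**PPAS1.** Protocol 12.2.3.1 has "Blood Sampling 0002A: Visit 1 + 30 days (± 21 days", whereas SAP 5.2.3.1 has +21 days only. SAP 5.7 lists changes to the planned analyses, and this is not among them.

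**Use of the sets.** SAP 5.2.4 runs all immunogenicity analyses on a PPAS, and SAP Table 5.2 places both hypothesis tests 30 days after the second vaccination. No sentence names PPAS2 as the primary set, but it is the only PPAS that holds this time point.

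**Discretionary exclusion.** A further PPAS2 bullet reads "Subject had other protocol violations that affected the subject's immune response, as determined by the clinical team before locking the database".

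**The concern.** The stated rule for the confirmatory set is three weeks wider, on the early side, than the window in which the sample was to be taken. Protocol 5.2.10 gives missed time windows as an example of significant non-compliance, so an early bleed is a deviation by the protocol's own terms. The bullet in PPAS2 that deals with sample timing nevertheless lets it through.

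Both tests are described as results 30 days after dose 2. As written, a Day 9 titre can enter either test as such a result. Whether it does depends on the clinical team deciding, child by child, that the immune response was affected, with a stated window that says Day 9 is acceptable.

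The SAP makes this harder to read as intended. It has the schedule's window in PPAS1, where no hypothesis is tested, and the wider one in PPAS2, where both are. Neither document explains the difference.

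**Working it through.** **1. Windows**

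| Source | Rule | Days after dose 2 |
|---|---|---|
| Procedure tables (both documents), protocol 5.1.4 | 30, +21 | 30 to 51 |
| PPAS2, protocol 12.2.3.2 and SAP 5.2.3.2 | 30 ± 21 | 30 − 21 = 9 to 30 + 21 = 51 |

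PPAS2 accepts 43 days and the schedule 22. The extra 21 are Day 9 to 29.

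**2. The plan's power figure**

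Inputs from SAP 5.5: 435 enrolled per arm, at most 40% non-evaluable, so 435 × 0.60 = 261; margin 10%; equal true rates of 97.7% (A), 97.8% (C), 93.3% (Y) and 86.7% (W). The one-sided 0.025 level follows from the 95% interval in SAP 5.1.1.2.

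Farrington-Manning power = Φ{(0.10 − 1.96·s₀)/s₁}, where s₀ uses the restricted estimates under a difference of −10 points and s₁ the true rates.

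- For W the restricted rates are 0.803 and 0.903.
- s₀ = √[(0.803·0.197 + 0.903·0.097)/261] = 0.0307.
- s₁ = √(2·0.867·0.133/261) = 0.0297.
- Power = Φ(1.34) = 91.0%.

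Y gives 99.0%, and A and C 100%. The product, assuming independence, is 90.1%, against 90.0% stated. The plan's figure reproduces, and the window is not an input to it.

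**3. What early bleeds could do (illustration)**

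Let f be the share of PPAS2 bled on Day 9 to 29, the same in both arms. The documents give neither f nor the effect of early sampling, so both are assumptions. The figures come from exact enumeration of the SAP 5.1.1.2 interval for W, with 261 per arm and a control rate of 86.7%.

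- Case A: true Day-30 difference −10 points, none in early bleeds. Observed difference −0.10(1 − f).
- Case B: true Day-30 difference −10 points, half of it in early bleeds. Observed difference −0.10 + 0.05f.
- Case C: no difference at Day 30, a 10-point deficit in early bleeds. Observed difference −0.10f.

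| f | Early bleeds per arm (261f) | A: false non-inferiority | B: false non-inferiority | C: W power |
|---|---|---|---|---|
| 0 | 0 | 2.6% | 2.6% | 91.6% |
| 1% | 3 | 2.7% | 2.6% | 91.0% |
| 2% | 5 | 2.9% | 2.7% | 90.3% |
| 5% | 13 | 3.6% | 3.0% | 88.3% |
| 10% | 26 | 4.9% | 3.6% | 84.2% |

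The 91.6% at f = 0 differs from the plan's 91.0% because it uses the planned test interval rather than the Farrington-Manning approximation. At f = 2% the shifts are 2.93 − 2.56 = 0.4 points of error and 91.6 − 90.3 = 1.3 points of power.

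**4. What a narrower window could cost**

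At 20% or 30% non-evaluable, 435 × 0.80 = 348 or 435 × 0.70 ≈ 304 per arm remain, both above 261. Only at the 40% ceiling does further exclusion cut below plan:

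| Removed | Per arm | Overall power |
|---|---|---|
| 0 | 261 | 90.1% |
| 1% | 258 | 89.7% |
| 2% | 255 | 89.3% |
| 5% | 247 | 88.2% |
| 10% | 234 | 86.1% |

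**The case against.** The best defence is that the two windows do different jobs. A visit window tells sites when to bleed; a per-protocol window says which deviations disqualify a sample. They may differ, and for PPAS2 the protocol and SAP agree exactly, so the set is prespecified and reproducible. On that reading the SAP's PPAS1 entry could be the slip, because the other three post-dose definitions all read ±.

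It can be added that every instruction to sites says +21, so early bleeds should be rare. The window applies equally to both arms, parents, investigators and laboratory staff are blinded, and the discretionary bullet operates before database lock within a review that protocol 11.3 calls blind. The larger figures above need about 26 children per arm bled against schedule, together with a strong effect of early sampling that nothing in the documents supports.

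Much of this stands: the effect may well be negligible, its direction is unknown, and there is some control over early bleeds. It does not remove the inconsistency. A deliberately wider window would need a reason, and neither document gives one. The SAP's own PPAS1 goes the other way. The discretionary bullet is a weak safeguard when the stated timing rule already accepts the sample.

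**Conclusion.** The point holds. In both documents the PPAS2 timing rule admits Day 9 to 29 samples that the schedule does not allow, and PPAS2 carries both non-inferiority tests. Groups 3 and 4 have the same mismatch, but their results are descriptive.

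The inconsistency is certain; its effect on the result is not known. If early bleeds make up 1 to 2% of the set, it is negligible. At 10%, error on W could rise from 2.6% to 4.9%, or W power fall from 91.6% to 84.2%, but only under the assumed contrasts between early and Day-30 responses. Planned sample size and power are unaffected. It should be fixed because it is a stated rule for the primary analysis set and the remedy is cheap.

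**What to change.** **If PPAS2 can still be changed blind.** Change ± 21 to +21 for BL0003 (Groups 1 and 2) and BL0002 (Groups 3 and 4) in SAP 5.2.3.2 and protocol 12.2.3.2. Bring protocol 12.2.3.1 into line with the SAP's PPAS1, and record all of this in SAP 5.7. Children bled early remain in FAS2, whose definition has no sampling window. The text change is one symbol per bullet, but the protocol edits are an amendment under protocol 5.4. The statistical cost is a few more exclusions, number unknown, which touches planned power only if fewer than 261 per arm remain.

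**If it cannot.** SAP 5.6 describes the data review partly in the past tense, and the documents do not settle whether a blind change is still possible. In that case keep PPAS2 as written, add a sensitivity analysis of both tests restricted to BL0003 on Day 30 to 51, and report the number of Day 9 to 29 samples by group. This costs one extra table and no power.

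If ± 21 is intended, the SAP should say so and explain why PPAS1 differs.
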